**Figure 3. Effects of NT—I7 on absolute lymphocyte counts, proliferation rates, and CD4+ and CD8+ T-cell subsets.**

#### 2.3.2.2 Completed Study GX-I7-CA-003

GA- I7-CA-003 was a Phase 1b, single-agent, open-label, 3+3 dose-escalation study to determine the Recommended Phase 2 Dose (RP2D) and to evaluate safety, tolerability, PK, and pharmacodynamics of NT-I7 in subjects with locally advanced or metastatic solid tumors. GX-I7 (an alternative name for NT-I7) was administered IM on Day 1 of each 21-day cycle at doses of 60  $\mu$ g/kg, 120  $\mu$ g/kg, 240  $\mu$ g/kg, 480  $\mu$ g/kg, 720  $\mu$ g/kg, 960  $\mu$ g/kg, 1200  $\mu$ g/kg, and 1700  $\mu$ g/kg.

Pharmacodynamic data from the study showed ALC and naïve/less differentiated memory subsets of CD4+ and CD8+ T cells increased in a dose-dependent manner after NT-I7 administration. T cell increases were most prominent in the 1200  $\mu$ g/kg and 1700  $\mu$ g/kg dose groups. The levels of endogenous IL-7 remained at normal levels without any significant change.

The dose-dependent increase in exposure with GX-I7 was observed in all dose groups. Following IM administration, the GX-I7  $T_{max}$  was 11 to 47.5 hours depending on dose, with an elimination half-life of 60.8 to 139.7 hours.  $C_{max}$  and  $AUC_{last}$  increased with increasing dose of study drug, and both increased in a dose-proportional manner.

In GX-I7-CA-003, immunogenicity was assessed by measuring ADAs and nAb on all subjects. No subject was positive 8 days after the first administration of NT-I7, and ADAs and nAb were detected in all subjects by the third administration of NT-I7 (regardless of dose or dosing

interval). All subjects remained positive for both while continuing to receive NT-I7. Endogenous IL-7 levels were maintained at normal levels without significant change, and there were no specific AEs related to ADA. The presence of ADAs did not appear to affect drug exposure, pharmacodynamic endpoints, or safety of the drug with repeated dosing in patients with solid cancers.

### 2.3.2.3 Other Studies

ABTC-1403 (also known as NIT-104) is an ongoing Phase 1 dose-escalation and pilot study of the effect of NT-I7 on CD4 cell counts in subjects with high grade gliomas and severe treatment-related CD4 lymphopenia after concurrent radiation therapy (RT) and treatment with temozolomide (TMZ). The study is ongoing in the U.S.

NIT-106 is a Phase 1b/2a, open-label study to evaluate anti-tumor efficacy and safety and tolerability of NT-I7 in combination with anti-PD-L1 (atezolizumab) in subjects with anti-PD-1/PD-L1 naïve or relapsed/refractory high-risk skin cancers.

NIT-109 is Phase 2 study of NT-I7 in combination with nivolumab in subjects with relapsed/refractory gastric or gastro-esophageal junction or esophageal adenocarcinoma who progressed on or were intolerant to 2 or more prior lines of systemic therapy.

NIT-110 is a multicenter, open-label, Phase 1b/2a study of NT-I7 in combination with pembrolizumab in subjects with relapsed/refractory advanced solid tumors.

NIT-112 is a multicenter, Phase 1b study evaluating safety, tolerability, and preliminary anti-tumor activity of NT-I7 administration following standard of care tisagenlecleucel CAR T cell therapy in subject with relapsed/refractory large B cell lymphoma.

NIT-116 is a multicenter, double-blind, randomized, placebo-controlled Phase 1, single dose, dose escalation study of NT-I7 in adults with mild COVID-19.

NIT-119 is a multicenter, open-label, single-arm Phase 2 study evaluating anti-tumor efficacy and safety of NT-I7 in combination with atezolizumab in subjects with previously untreated, PD-L1-expressing, locally advanced or metastatic non-small cell lung cancer.

More details are provided in the NT-I7 Investigator's Brochure.

### 2.3.3 Benefits and Risks Conclusions

Safety, pharmacodynamic, and PK data for NT-I7 are available from two completed and seven ongoing studies. Based on the available data, it can be concluded that:

- 1) NT-I7 was well tolerated in healthy volunteers and adult subjects with advanced solid tumors;
- 2) NT-I7 was well tolerated in combination with checkpoint inhibitors (CPIs) in adult

patients with relapsed/refractory solid tumors;

- 3) NT-I7 was slowly absorbed and eliminated, resulting in a flat PK profile, regardless of route of administration;
- 4) IM administration of NT-I7 resulted in more rapid absorption and had higher exposure to NT-I7 than did SC administration;
- 5) NT-I7 led to a dose-dependent increase in CD4+ and CD8+ T cells (naïve T cells, TSCM, TEM, TCM, TEMRA) and NK cells, but there was no dose-dependent increase in B cells;
- 6) IM administration of NT-I7 resulted in a more pronounced increase in lymphocytes over SC administration.

The well-tolerated safety profile seen with NT-I7 in humans and the ability of NT-I7 to increase naïve T cells, TEM, TCM, TEMRA in cancer patients as well as the promising preclinical data of NT-I7 in combination with CPIs support further clinical investigation of NT-I7 in cancer patients to enhance anti-tumor activity.

More detailed information about the known and expected benefits and risks and reasonably expected AEs may be found in the NT-I7 IB.

## 2.4 Rationale

[figure not shown]
### 2.4.1 Risk Benefit Analysis in HIV associated Kaposi Sarcoma

Cancer is the leading cause of death in people with HIV. KS is associated with 40% mortality in HIV clinics in the US and Canada. Scalable T cell modulating therapies with minimal toxicities are highly desirable for KS. Based on the literature to date, the benefits of an effective immunotherapy for KS outweigh the theoretical risk of increasing the HIV reservoir. We hypothesize that NT-I7 will have a favorable therapeutic index in people with KS. Optimizing the dosing schedule will be important in the evaluation of NT-I7 in this patient population. CD4 lymphocytopenia in people living with HIV has a specific etiology and is substantially unique from other cancer populations. KS responses based on changes in CD4 counts have been established in the setting of HIV, distinguishing it from other cancers. The dosing schedule for this proposal is based on PD data from short acting IL-7 in people living with HIV and no cancer (Figure 1). In this study by Thiébaut *et. al.*, participants received weekly IL-7 for 3 weeks, had a peak CD4 count on week 4 that gradually declined over time. The CD4 count at week 4 decreased from peak but remained elevated compared to baseline. NT-I7 (IL-7-Fc) has much longer serum half-life than IL-7. The proposed schedule was suggested by NeoImmuneTech (NIT). NIT has preclinical data showing that over stimulation from too frequent dosing might have a negative effect. At present there does not appear to be a compelling rationale for more frequent dosing in HIV associated cases. This Phase I study will evaluate the kinetics of peripheral and tumor T cell expansion after the first and second doses of NT-I7. Evaluation of the safety of NT-I7 will include stopping rules for clinically significant events related to treatment of HIV (i.e., induction of HIV viremia with a drug resistant strain; clinical AIDS-defining events attributed to HIV viremia and associated immune decline despite demonstration of HIV adherence) as well as detailed evaluation of the effects on the HIV reservoir.

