## 5.2 Summary Table(s) for Research Biopsies

Table 4. Mandatory Biopsy #1 Collection Summary.

Biopsy #: 1 (Mandatory)				
Trial Time Point: Baseline				
Biopsy Definition: Research – No Clinical Impact (All cores from a single biopsy procedure impact research goals, but do not directly impact patient care or benefit the patient.)				
Core Priority	Use in the Trial	Biomarker Name(s)	Tumor Content Required	Post-Biopsy Processing
1	Integrated	TCR Clonality	[5-25% or greater]	Formalin
2	Exploratory	CD3, CD8, CD4, CD79A CD68, PD-1, FoxP3 and MHC Class I	[5-25% or greater]	Formalin
1	Exploratory	Gene Expression Profiling	[5-25% or greater]	Formalin

Table 5. Mandatory Biopsy #2 Collection Summary.

Biopsy #: 2 (Mandatory)				
Trial Time Point: 9 weeks (Post-treatment tumor biopsy will be obtained prior to dosing on Cycle 2, Week 9, Day 1 or at the End of Treatment visit, whichever occurs first.)				
Biopsy Definition: Research – No Clinical Impact (All cores from a single biopsy procedure impact research goals, but do not directly impact patient care or benefit the patient.)				
Core Priority	Use in the Trial	Biomarker Name(s)	Tumor Content Required	Post-Biopsy Processing
1	Integrated	TCR Clonality	[5-25% or greater]	Formalin
2	Exploratory	CD3, CD8, CD4, CD79A CD68, PD-1, FoxP3 and MHC Class I	[5-25% or greater]	Formalin
1	Exploratory	Gene Expression Profiling	[5-25% or greater]	Formalin

Table 6. Optional Biopsy #1 Collection Summary.

Biopsy #: 1 (Optional)				
Trial Time Point: 13 weeks (4 weeks after second dose)				
Biopsy Definition: Research – No Clinical Impact (All cores from a single biopsy procedure impact research goals, but do not directly impact patient care or benefit the patient.)				
Core Priority	Use in the Trial	Biomarker Name(s)	Tumor Content Required	Post-Biopsy Processing
1	Integrated	TCR Clonality	[5-25% or greater]	Formalin
2	Exploratory	CD3, CD8, CD4, CD79A CD68, PD-1, FoxP3 and MHC Class I	[5-25% or greater]	Formalin

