## 6. TREATMENT PLAN

Based on the pharmacodynamic data obtained from the GX-I7-CA-003 study (Q3W) dosing and preliminary data from other ongoing studies with less frequent dosing schedules, NT-I7 can be given less frequently than every three weeks and more frequently than every twelve weeks (e.g., Q9W), and will still lead to similar changes in the ALC and other peripheral blood T-cell subsets.

This is a Phase I, open-label, multicenter study to determine the safety and efficacy of NT-I7 in HIV-negative and HIV-positive patients with KS. A traditional 3+3 design (Figure 6) will be used, with DLT window being the first 28 days of study treatment. Three dose levels of NT-I7 will be administered, 480  $\mu$ g/kg, 960  $\mu$ g/kg and 1200  $\mu$ g/kg injected on Day 1  $\pm$  2 days of every cycle (every 9 weeks).

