**Figure 6: 3+3 Phase 1 study design schema.**

All participants enrolled into this study will receive NT-I7 IM injections at the scheduled dose level (Table 8). Participants will be treated at a given dose level every 9 weeks for up to 27 weeks (4 doses) and followed for an additional 12 months. NT-I7 will be held if the ALC is greater than 10,000 cells/ $\mu$ L at the time of administration. There will be no intra-participant dose escalation.

Three participants will be enrolled at dose level 1. If 0 of 3 have a DLT (described in [Section 6.2](#)), dosing will escalate to the next dose level. If 1 of 3 have a DLT, that dose level will expand

to 6 participants. If 1 of 6 participants has a DLT, dosing will escalate to the next highest level. If 0-1 participant has a DLT at dose level 3, an additional 3 participants will be treated at that level.

If two participants have a DLT at dose level 1 or dose level -1, dosing will de-escalate to the next lowest level. Dose levels -1 (360  $\mu\text{g}/\text{kg}$ ) and -2 (240  $\mu\text{g}/\text{kg}$ ) have been defined if there is unexpected toxicity at dose level 1.

The recommended phase 2 dose (RP2D) will be selected according to the following logic, taking into account the MTD determination from the Dose Escalation Phase (Phase I) and the Maximum Effective Dose (MED) level which is defined as the dose level at which maximum effects on peripheral blood T-cell levels and intratumor T-cell levels are observed. The intratumor T-cell levels will dominate if the peripheral blood and intratumor T-cell levels differ. The available data will be assessed by the Protocol PI(s), the Protocol Chair, and the CITN Central Operating and Statistical Center (COSC) to select the RP2D.

- If the MTD is determined AND
  - MTD = MED, then the RP2D = MTD = MED
  - MTD > MED, then the RP2D = MED
- If the MTD is not reached, then the RP2D = MED

Treatment emergent adverse events will be tabulated according to grade and attribution ( $\geq$  possibly attributed to NT-I7 versus  $\leq$  unlikely related to NT-I7).

Response to therapy will be evaluated by clinical exam using AIDS Clinical Trials Group Criteria ACTG criteria at baseline, 9 weeks, 13 weeks, 18 weeks, 27 weeks, and 36 weeks as outlined in the Trial Schema.

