### 6.1.2 Other Procedures: Biopsy (core needle, punch or excisional)

Biopsy/tumor tissue will be obtained by punch biopsy, incisional or excisional biopsy. Core needle biopsy or excisional biopsy may be acceptable for visceral lesions depending on clinical circumstance.

**Note:** Baseline tumor biopsy (fresh) may be obtained up to 28 days prior to treatment initiation.

An archival tumor sample obtained within 1 year of screening is allowed if the pre-treatment biopsy is deemed unsafe or technically not feasible.

Tissue based studies will be performed on mandatory biopsies collected at baseline and at 9 weeks, with an optional biopsy at 13 weeks. Biopsy scheduled for collection at 9 weeks will be obtained prior to dosing on Cycle 2, Week 9, Day 1 or at the End of Treatment visit, whichever occurs first. Effect on tumor microenvironment will be assessed by multi-spectral IHC on serial biopsies.

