#### 9.4.3 Kinetics of CD4+ and CD8+ T cells in blood, and on levels and phenotype within tumors, using flow cytometry and immunohistochemistry, respectively.

It is hypothesized that NT-I7 will lead to T cell expansion over the first 4-8 weeks after administration and that increases will be measurable in the blood using total blood counts with automated differentials and flow cytometry and in tumors by immunohistochemistry at 9 weeks. For blood measurements, ALC will be measured primarily, while absolute CD4+ and CD8+ T cell will be evaluated secondarily. Tumor infiltrating lymphocytes (TILs) will be evaluated quantitatively (cells/hpf) with qualitative annotation of the pattern of distribution.

For analysis of circulating lymphocytes we will first describe fold-change (median and range) in blood ALC from pre-administration to each time point following first administration (1, 4, and 9 weeks), and by category of selected participant characteristics (e.g., dose level, age [by decade], sex, HIV status, prior systemic therapy, and in HIV+, by CD4+ T cells (< versus  $\geq$  200 cells/uL). More formally, we will explore multilevel negative binomial regression to estimate fold-change from pre-administration, adjusted for NT-I7 dose, HIV status, prior therapy, and baseline CD4+ T cell counts. In this analysis, ALC is the dependent variable and a generalized linear mixed model is applied with time from administration (weeks), an indicator of first or second administration, and gap between first and second administration as independent variables of interest in addition to adjustment variables. A random intercept is included for each participant to incorporate correlation between T cell counts from the same participant. The exponentiated fixed-effects model coefficients estimate fold-change from baseline with 95% CIs for a representative participant.

The same analytic approach will be applied to analysis of CD4+ and CD8+ T cells separately, and to TIL counts.

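### The tumor biopsy schedule cannot separate a second-dose effect from time since dose, so the second-dose and gap terms that Section 9.4.3 carries over to TIL counts are not interpretable

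*Combined protocol and SAP*

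**What the plan says.** Section 2.4.1 sets the aim for blood and tumor together: "This Phase I study will evaluate the kinetics of peripheral and tumor T cell expansion after the first and second doses of NT-I7".

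Section 6.1.2 gives the tumor sampling: "Tissue based studies will be performed on mandatory biopsies collected at baseline and at 9 weeks, with an optional biopsy at 13 weeks". The week-9 sample is taken "prior to dosing on Cycle 2, Week 9, Day 1 or at the End of Treatment visit, whichever occurs first". Doses are nine weeks apart (Section 6), and Table 6 in Section 5.2 places the optional biopsy four weeks after the second dose. The study calendar agrees. No biopsy is scheduled four weeks after dose 1 or nine weeks after dose 2.

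Section 9.4.3 states its tumor hypothesis at 9 weeks. For blood ALC it first describes fold-change after the first administration. It then explores a negative binomial mixed model with time from administration in weeks, "an indicator of first or second administration, and gap between first and second administration as independent variables of interest". It does not say whether time is linear or categorical. It ends: "The same analytic approach will be applied to analysis of CD4+ and CD8+ T cells separately, and to TIL counts".

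Section 6 bases the maximum effective dose (MED) on blood and intratumor T-cell levels and adds: "The intratumor T-cell levels will dominate if the peripheral blood and intratumor T-cell levels differ". It names no biopsy time for that comparison.

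**The concern.** Blood is drawn at several times after dose 1 and again at four and nine weeks after dose 2, so a dose-number effect can be compared at matched times. Tumor has no such matching. The week-13 biopsy is the only scheduled sample after dose 2 and also the only one at four weeks after a dose. A change at week 13 could mean that the second dose acts differently, or only that four weeks is a different point on the same curve. The model nevertheless has a coefficient that would be read as the effect of the second dose.

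Two things are at stake. First, a TIL second-dose fold-change with a confidence interval could be reported when the data do not support it. Second, tumor levels outrank blood levels in setting the MED. If the biopsy time for that comparison is left open, dose levels with different uptake of the optional biopsy could be compared at different times.

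**Working it through.** The plan states no effect size, power or sample size for TIL, so there is no figure to reproduce. The check is whether the scheduled biopsies can identify the model's terms.

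**Inputs from the documents.** Tumor samples as (weeks since latest dose, second-dose indicator): baseline (0, 0); week 9 before dose 2 (9, 0); week 13 (13 − 9 = 4, 1). Blood samples on the same coding: (0, 0), (1, 0), (4, 0), (9, 0), then (4, 1) at week 13 and (9, 1) at week 18.

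**Step 1. Rank of the fixed-effects design.**

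| Model | Parameters | Rank |
|---|---|---|
| Tumor: intercept, linear time, second dose | 3 | 3 |
| Tumor: intercept, categorical time (4, 9 weeks), second dose | 4 | 3 |
| Tumor: linear time, second dose, gap constant at 9 weeks | 4 | 3 |
| Blood: intercept, categorical time (1, 4, 9 weeks), second dose | 5 | 5 |

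In blood the dose-number effect is estimable. In tumor it is not, except with linear time and no gap term, and that mean model is saturated: three visit means and three coefficients.

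**Step 2. What the linear-time coefficient measures.** Let f(w) be the mean log TIL count at study week w. Solving the three equations gives

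second-dose coefficient = f(13) − f(0) − (4/9)[f(9) − f(0)].

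This is the week-13 change minus what a straight line from week 0 to week 9 predicts at four weeks. No scheduled sample tests that line.

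**Step 3. Result when both doses act identically.** Assume each dose multiplies TIL by a at 4 weeks and by r at 9 weeks, with no carry-over. The reported ratio is a / r^(4/9); an analysis free of the problem would give 1.00. The documents do not give a or r, so these are assumptions shown over a range.

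| a (4 weeks) | r (9 weeks) | Calculation | Reported ratio |
|---|---|---|---|
| 2 | 1 | 2 / 1 | 2.00 |
| 2 | 1.2 | 2 / 1.084 | 1.84 |
| 2 | 1.5 | 2 / 1.197 | 1.67 |
| 1.08 | 1.2 | 1.08 / 1.084 (log-linear growth) | 1.00 |
| 1.5 | 3 | 1.5 / 1.629 | 0.92 |
| 1 | 2 | 1 / 1.361 | 0.73 |

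If the first dose's week-9 effect carries over multiplicatively, each ratio is multiplied by r: 1.84 becomes 2.21 and 0.73 becomes 1.47.

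**Step 4. Likely direction.** Section 2.3.2.1 reports that blood ALC peaked about 3 weeks after dosing. If TILs behave similarly, a exceeds r and the bias is upward. Section 9.4.3 itself expects T-cell expansion over the first 4–8 weeks, which does not settle the shape in tumor.

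**Step 5. Would sampling noise hide it?** In a simulation with 18 participants (assumed mean count 30, dispersion 0.2, between-patient log-SD 0.5; a within-patient log-linear fit standing in for the mixed model), a = 2 and r = 1.2 gave a median ratio of 1.82, with p < 0.05 in 98% of runs (81% if half gave the optional biopsy). Under log-linear growth the median was 1.00, with p < 0.05 in 7%.

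**The case against.** The strongest reply is that little hangs on this model. Section 9.4.3 introduces it as exploratory, its tumor hypothesis is at 9 weeks, and its descriptive step, if carried over to TIL, is already close to a week-9/baseline comparison by dose level. Secondary objective 1.2.4 names blood only, and the sentence in 2.4.1 is rationale rather than an objective. All of this is true and limits the severity. It does not rescue the second-dose term, which the plan lists among its variables of interest and then extends to TIL.

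The schedule is also less rigid than three fixed points. The End of Treatment fallback gives earlier samples after dose 1, and holds can move dose 2 and vary the gap. But early stoppers are a selected group, and neither feature provides scheduled tumor samples at matched times after each dose.

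A reader might infer two stronger things. The first is that the model will report a false second-dose effect. The documents do not support that: the form of time is open, and the bias may be upward, nil or downward.

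The second is that voluntary week-13 biopsies would decide which dose level becomes the MED. Section 6 neither links the MED to this regression nor says that the larger visit mean is used; it leaves the recommended dose to review of the available data. Even under such a rule, strong distortion was seen only where some dose levels had no week-13 biopsy at all. I simulated three equally active levels of 3, 3 and 6 participants, with true fold-changes of 1.2 at week 9 and 2 at week 13. With optional biopsies at every level (2, 2, 4 or 2, 1, 3), level 1 looked best in about 32–36% of runs, against 35% from week 9 alone. What stands is narrower: the biopsy time for the MED comparison is unspecified and should be fixed.

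**Conclusion.** The concern holds as a defect in the stated TIL analysis. On the planned schedule, the second-dose TIL term is not estimable with categorical time or a constant gap. With linear time and no gap term, it depends entirely on a straight line that the scheduled biopsies cannot test. This conclusion needs only the biopsy and dosing schedule.

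The size of any bias is conditional. For identical doses without carry-over, the examples run from 0.73 to 2.00. An upward bias is likely if TILs, like blood ALC, peak before week 9, but no TIL time course is given. No effect on the recommended Phase 2 dose is shown; the MED comparison is merely left open to a mix of biopsy times. The change is worth making because the stated model gives an uninterpretable result and the plan's own week-9 hypothesis supplies a sound replacement.

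**What to change.** 1. **Section 9.4.3.** For TIL, drop the administration indicator and the gap term. Analyze the paired log-ratio of week 9 to baseline, by dose level. Report End of Treatment biopsies taken before week 9 separately, and flag participants whose baseline is archival tissue. Report week 13 descriptively, in participants with all three biopsies.
2. **Section 6.** State that intratumor T-cell levels are compared across dose levels for the MED at the same mandatory time point, week 9 against baseline, so that uneven uptake of the optional biopsy cannot affect the comparison.
3. **Section 2.4.1.** Restate the tumor aim as change after the first dose, with descriptive week-13 data. The aim for blood can stay.

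The cost is protocol and SAP wording, with no new samples or visits. The one downside is that week-13 tumor data become descriptive. Keeping a second-dose tumor aim would instead require biopsies at a matching time after both doses.
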